##### Metabolism

Apalutamide is primarily metabolized by CYP2C8 and CYP3A4 to form active metabolite, N-desmethyl apalutamide. The contribution of CYP2C8 and CYP3A4 in the metabolism of apalutamide is estimated to be 58% and 13% following single dose but changes to 40% and 37%, respectively at steady state. Apalutamide represented 45% and N-desmethyl apalutamide represented 44% of the total AUC following a single oral administration of radiolabeled apalutamide 240 mg.

##### Contraindications

Apalutamide can cause fetal harm and potential loss of pregnancy.

Apalutamide is contraindicated for use in pregnant women because the drug can cause fetal harm and potential loss of pregnancy. Apalutamide is not indicated for use in females, so animal embryo-fetal developmental toxicology studies were not conducted with apalutamide. There are no human data on the use of apalutamide in pregnant women. Based on its mechanism of action, apalutamide may cause fetal harm when administered during pregnancy.

#### Formulation, Appearance, Packaging, and Labeling

Apalutamide is supplied as 60 mg tablets for oral administration. The 60-mg tablets consist of apalutamide drug substance, which is a white to slightly yellow powder. Apalutamide tablets (60 mg) are packaged in 120-count, 160 cc HDPE bottles with CRC and include desiccant, and should at all times be kept in the original packaging.

#### Availability

Apalutamide is being obtained as study supply provided by Janssen.

#### Storage and Handling

Detailed information on handling and storage conditions will accompany the clinical drug supplies to the clinical study site(s). The storage conditions and expiry will be indicated on the label of the drug product.

#### Side Effects

Complete and updated adverse event information is available in the Investigational Drug Brochure (IB) and/or product package insert.

#### Dosage and Administration

Apalutamide is administered orally on a continuous once daily dosing schedule. Each cycle of drug administration consists of 28 days. Doses from 30 to 480 mg daily were tested in the Phase 1 portion of the first clinical study (Study ARN-509-001). The therapeutic dose is 240 mg (4 x 60 mg tablets) once daily. Apalutamide can be taken with or without food.

For patients who have difficulty swallowing tablets whole, the recommended dose of apalutamide tablets may be mixed with 4 ounces (120 mL) of applesauce. Do not crush the tablets. Stir applesauce upon introduction of whole tablets as well as at 15 minutes and 30 minutes afterwards until tablets are dispersed (well mixed with no chunks remaining). Using a spoon, swallow the mixture right away. Rinse the mixture container with 2 ounces of water and immediately drink the contents. Repeat the rinse with 2 ounces of water one more time to ensure the whole dose is taken. The mixture should be consumed within one hour of preparation.

### **4.1.2 Cetrelimab**

#### Classification

Antineoplastics; immunotherapies; monoclonal antibodies

Cetrelimab is a fully human IgG4 kappa mAb against PD-1 with an S228P stabilizing mutation in the hinge region. Cetrelimab is produced in a Chinese hamster ovary cell line.

#### Mechanism of Action

Antibody-dependent cell cytotoxicity; programmed cell death-1 receptor antagonists; T lymphocyte stimulants

#### Formulation, Appearance, Packaging, and Labeling

The drug product (DP) is supplied as a lyophilized DP that, upon reconstitution, results in a liquid for IV infusion.

#### Availability

Cetrelimab is being obtained as study supply provided by Janssen.

#### Storage and Handling

Drug product should be stored at 2°C to 8°C and protected from light.

#### Side Effects

Complete and updated adverse event information is available in the Investigational Drug Brochure (IB) and/or product package insert.

#### Physical and Chemical Characteristics

Cetrelimab has a molecular weight of approximately 148,000 Daltons and an isoelectric point of 7.2 for the major peak. The absorptivity constant for cetrelimab at 280 nm was determined to be 1.36 (mg/mL)-1cm-1.

#### Formulation Information

The DP has an approximate pH of 6.5 and does not contain a preservative. The fill volume is 8.6 mL prior to lyophilization. Post lyophilization and prior to use, the lyophilized DP is reconstituted with 8 mL of sterile water for injection (sWFI). The dissolution of the lyophilized cake with the sWFI yields a final concentration of 30 mg/mL. The lyophilized DP includes 7.5% overfill to allow withdrawal of up to 360 mg/vial.

The DP is filled aseptically in a glass vial. The composition of the DP is provided in Table 2.

Table 2 Composition and Concentration of Lyophilized Drug Product

Ingredient	Targeted Fill Amount per Vial a (mg)	Targeted Amount per mL (mg/mL) b
Cetrelimab	258	30
L-Histidine	9.89	1.15
L-Histidine monohydrochloride monohydrate	4.64	0.54
Sucrose	688	80
Polysorbate 20 c	1.32	0.4 c
EDTA, disodium salt, dihydrate crystal	0.17	0.02
Water for injection	Reconstitute with 8.0 mL	NA

a The target fill volume is 8.6 mL. This includes a 0.6 mL overfill to allow withdrawal of at least 240 mg/vial (8.0 mL volume).

b Target amount per mL post reconstitution.

c Vegetable based; low peroxide.

NA = Not applicable

EDTA = ethylenediaminetetraacetic acid

## 4.2 Accountability Records for Investigational Products

UCSF Investigational Drug Services (IDS) will manage drug accountability records for UCSF.

## 5 Treatment Plan

### 5.1 Dosage and Administration

Treatment will be administered on an outpatient basis.

The starting dose of apalutamide will be 240 mg daily for patients not on apalutamide prior to study enrollment. For patients on apalutamide during Screening will be permitted to continue dose prior to enrollment.

Cetrelimab will be given at the recommended phase 2 dose of 480 mg via IV on day 1 of every 28-day treatment cycle. C1D1 dose will be administered over a 60-minute infusion. In the absence of infusion-related reactions, subsequent infusions may be administered IV over 30 minutes, depending on the volume administered. Subjects should be carefully observed during cetrelimab infusions. Trained study staff at the clinic should be prepared to intervene in case of an IRR. Resources necessary for resuscitation (e.g., agents such as epinephrine and aerosolized bronchodilator, medical equipment such as oxygen tanks, tracheostomy equipment, and a defibrillator) must be available at the bedside. Attention to staffing should be considered if multiple subjects will be dosed at the same time. If an IRR develops, then the infusion should be temporarily interrupted or slowed down and the guidelines in Section 6 should be followed to manage the IRR.

For the first infusion, vital signs should be assessed before the start of the infusion, every 15 to 20 minutes during the infusion, at the end of infusion, and approximately 2 hours after the end of

infusion. After the completion of the first infusion the subject may be discharged if considered clinically stable and all other study procedures have been completed. During subsequent infusions of cetrelimab, vital signs should be assessed pre-dose, once during infusion, and at the end of infusion. Cetrelimab infusions will be prepared and administered as described in the Investigational Product Preparation Instructions (IPPI).

**Table 5.1 Regimen Description**

Investigational Product	Premedication; precautions	Starting Dose	Route	Schedule	Cycle Length
Cetrelimab	See below*	480 mg	IV	Day 1	28 days
Apalutamide	See below*	240 mg	Oral	Daily	

\* During the first 2 cycles of study treatment, all subjects will receive prophylactic treatment with an oral H1 receptor antagonist (e.g., cetirizine, fexofenadine, loratadine) plus an H2 receptor antagonist (e.g., famotidine) plus montelukast at 10 mg daily on a continuous basis, starting at Cycle 1 Day 1. That treatment may be discontinued after Cycle 3 Day 1 at the discretion of the investigator and so long as the subject does not experience rash, pruritus, or other hypersensitivity manifestations during the first 2 cycles of treatment (see below for management of drug-related rash).

## 5.2 Dose Modifications and Management of Toxicity

Dose interruptions for up to 28 days are allowed. For treatment interruptions lasting > 28 days, resumption of treatment is only allowed if patients are experiencing clinical benefit and only upon approval of Principal Investigator.

If one or more agent(s) is permanently discontinued due to AE, the patient may continue to receive the other medication(s) within regimen.

### 5.2.1 Retreatment Criteria for Cetrelimab and Apalutamide

**Table 5.2 Retreatment Criteria**

Adverse Event	Requirements before each study agent administration
Absolute neutrophil count	$\geq 1.0 \times 10^9/L$
Platelet count	$\geq 50 \times 10^9/L$ with or without platelet transfusions and/or growth factors
Hemoglobin	$\geq 8.0 \text{ g/dL}$ with or without transfusion, growth factors, or both
Fasting glucose, if prompted by HbA1c	$\leq 250 \text{ mg/dL}$
Hyperthyroidism	Grade $\leq 2$
AST and ALT	$\leq 3 \times \text{ULN}$ ( $\leq 5 \times \text{ULN}$ for patients with liver metastases)
Total bilirubin	$\leq 1.5 \times \text{ULN}$
Rash	Grade $\leq 2$
Other clinically significant toxicity 	Recovery to Grade $\leq 1$ or baseline

### 5.2.2 Dose Delay for Cetrelimab

Dose reduction of cetrelimab is not permitted. Treatment delay of cetrelimab is required until re-treatment criteria are met (Table 5.2) and for any of the following AEs:

- Grade 2 pneumonitis (recurrent Grade 2 or Grade  $\geq$  3 pneumonitis, cetrelimab must be permanently discontinued)
- Grade 2 or 3 diarrhea or colitis
- Grade 2 nephritis with creatinine  $>$  1.5 – 3 x ULN
- Grade 2 or 3 creatinine elevation
- Grade 2 elevation in AST or ALT except for patients with liver metastases at baseline, or total bilirubin 1.5 – 3 x ULN
- Grade 2 toxicity related to treatment with cetrelimab that is intolerable or persistent (lasts  $>$  28 days)
- Symptomatic endocrinopathies (hypothyroidism, hyperthyroidism, hypophysitis, adrenal insufficiency diabetes)
- Grade 3 rash
- Other Grade 3 treatment related toxicity assessed as related to cetrelimab

If a cetrelimab dose must be delayed by more than 2 weeks, administration should continue at the next planned dosing date and the dose will be considered a missed dose.

Study treatment with cetrelimab should be permanently discontinued for any of the following:

- The investigator believes that for treatment-emergent toxicity it is in the best interest of the subject to discontinue study treatment
- Grade 4 toxicities except for:
  - endocrinopathies that are controlled with replacement hormones
  - Grade 4 hematologic toxicities that resolve in less than 7 days may not result in study treatment discontinuation at the discretion of the treating physician.
- Grade 2 or 3 irAEs that persist despite treatment modifications or corticosteroid dosing cannot be reduced to  $\leq$  10 mg prednisone or equivalent per day within 12 weeks
- A treatment-related AE does not resolve to Grade  $\leq$  1 within 12 weeks of the last dose of study drug unless otherwise agreed to by the sponsor medical monitor and the investigator based on evidence of clinical benefit
- Any non-hematological treatment-related event occurs a second time at Grade  $\geq$  3 severity
- Grade  $\geq$  3 (or recurrent Grade 2) pneumonitis
- Grade  $\geq$  3 nephritis with creatinine  $\geq$  3xULN
- Grade  $\geq$  3 elevation of AST or ALT  $>$  5xULN or total bilirubin  $>$  3xULN
  - For subjects with baseline Grade 2 elevation of AST or ALT due to liver metastasis, only Grade  $\geq$  3 elevations that are  $\geq$  50% of baseline for  $\geq$  7 days will require discontinuation of study treatment
- Grade  $\geq$  3 infusion-related reactions (IRRs)
- Immune-mediated encephalitis

Once a subject discontinues treatment, the subject may not be retreated with the study drug.

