## 5.4 Management of Rash

Interventions for the management of skin rash are listed in Table below. Document skin rash of any type or grade by de-identified photographs.

For skin rash with any component of desquamation, mucosal involvement, or pustules:

- Stop dosing with apalutamide and cetrelimab
- Refer to dermatologist for evaluation
- Consider skin biopsy in patients experiencing Grade  $\geq 2$  rash, if clinically indicated per conventional (standard of care) management.

*OPTIONAL: In the event that one or more standard of care skin biopsies are conducted, extra tissue may be collected for research (immune correlate assay to explore the mechanism of skin rash) only for patients who give optional consent for the extra tissue collection. Refer to the Lab Manual and Section 6.4.5 for additional information.*

Management of Drug Related Rash	
Grade 1	
 
• Reduce apalutamide dose by one dose level
 
• Continue cetrelimab at current dose
 
• Initiate oral corticosteroids. Taper corticosteroid doses as clinically indicated while monitoring clinically for worsening symptoms
 
• Consider topical steroid cream
 
• Reinitiate oral H1 receptor blockers, if previously discontinued
 
• Consider re-starting H2 receptor blockers and/or montelukast, if previously discontinued
 
• Monitor for change in severity
 

Grade 2 (or symptomatic grade 1 a )	
 
• At principal investigator discretion, hold cetrelimab and apalutamide for up to 28 days and reinitiate when rash Grade is ≤1
 
• Reduce apalutamide dose by one dose level
 
• Initiate oral corticosteroids or consider escalating corticosteroid dose if already prescribed. Taper corticosteroid doses as clinically indicated while monitoring clinically for worsening symptoms
 
• Consider topical steroid cream
 
• Reinitiate oral H1 receptor blockers, if previously discontinued
 
• Consider re-starting H2 receptor blockers and/or montelukast, if previously discontinued
 
• Monitor for change in severity
 

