Grade ≥ 3 b	
 
• Hold cetrelimab and apalutamide for up to 28 days and reinitiate when rash
 
• Grade is ≤1; if after 28 days, the rash has not resolved to Grade ≤1, contact the sponsor to discuss further management and possible discontinuation of study drug
 
• Reduce apalutamide dose by one dose level at time of re-initiation
 
• Initiate oral corticosteroids or consider escalating corticosteroid dose if already prescribed. Taper corticosteroid doses as clinically indicated while monitoring clinically for worsening symptoms
 
• Consider topical steroid cream
 
• Initiate oral H1 and H2 receptor blockers and montelukast, if previously discontinued
 
• Monitor for change in severity
 
• Consider early referral to dermatologist
 

a. Patient presents with other rash-related symptoms such as pruritus, stinging, or burning

b. If there is blistering or mucosal involvement, stop cetrelimab and apalutamide dosing immediately.

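### The Grade ≥3 rash instructions (5.4) can restart cetrelimab in two situations where 5.2.2 stops it permanently: a second Grade ≥3 rash and a Grade 4 rash

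*Combined protocol and SAP*

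**What the plan says.** **Section 5.2.2 (cetrelimab).** Grade 3 rash is on the list of events that require a delay. A separate list opens with "Study treatment with cetrelimab should be permanently discontinued for any of the following". Two of its items matter here:

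- "Grade 4 toxicities except for" two named exceptions: endocrinopathies controlled by hormone replacement, and hematologic toxicity that resolves in under 7 days.
- "Any non-hematological treatment-related event occurs a second time at Grade" 3 or higher.

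The section closes with "Once a subject discontinues treatment, the subject may not be retreated with the study drug".

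**Section 5.4 (drug-related rash table, Grade ≥3 row).** The instruction is "Hold cetrelimab and apalutamide for up to 28 days and reinitiate when rash" is Grade 1 or lower, with apalutamide reduced one level at restart. If the rash has not reached Grade 1 by 28 days, the site is to "contact the sponsor to discuss further management and possible discontinuation of study drug".

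**Stops within 5.4.** These depend on the appearance of the rash. The lead-in, "For skin rash with any component of desquamation, mucosal involvement, or pustules", stops both drugs. Footnote b to the Grade ≥3 row adds: "If there is blistering or mucosal involvement, stop cetrelimab and apalutamide dosing immediately".

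**The concern.** The two sections give different orders for the same patient. The Grade ≥3 row covers Grade 4 and does not separate a first episode from a later one, so on its face it restarts cetrelimab after either. Section 5.2.2 forbids a restart after either.

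An investigator who manages rash from the rash table could therefore re-expose a patient to a checkpoint inhibitor when another section of the same protocol bars it. Two investigators could also treat identical patients differently while each follows a written rule. Oversight may come too late: Appendix 2, section 3.1 has the Site Committee review Grade 3–5 events monthly, but section 5.1 gives cetrelimab every 28 days, so a restart can precede the review.

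This does not touch the Simon design, the type I error, the power or the definition of composite response.

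**Working it through.** The plan states no figure on this point, so there is none to reproduce. The check compares the two texts case by case and then sizes the population that enters the row.

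**Side by side, for rash that settles to Grade 1 or lower within 28 days and lacks desquamation, pustules, blistering and mucosal involvement**

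| Drug-related rash | 5.4, Grade ≥3 row | 5.2.2 | Agree? |
|---|---|---|---|
| First episode, Grade 3 | Hold, restart | Delay | Yes |
| Second episode, Grade ≥3 | Hold, restart | Permanent stop, no retreatment | No |
| First episode, Grade 4 | Hold, restart | Permanent stop, no retreatment | No |

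**Does other text settle the order?**

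- *5.2.3* sends rash management to 5.4, but it is written for apalutamide. 5.2.2 has no matching deferral for cetrelimab, and 5.4 does not point back to 5.2.2.
- *Table 5.2* sets conditions before each administration. For rash it tests current grade (2 or lower). It does not look at past grade or number of episodes, so it would pass both conflict cases.
- *The stops in 5.4* depend on the appearance of the rash. None is tied to Grade 4 or to recurrence, and none says the stop is permanent.
- *The 28-day sponsor contact* applies only to a rash that has not resolved.
- *7.3.5* allows re-challenge for selected adverse events after the product was stopped. It does not exclude stops made under 5.2.2, so it does not settle the order either.

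**How many patients enter the row**

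Inputs are from section 1.6: 27 patients on the combination; Grade ≥3 rash in 37.0%; six discontinuations for an adverse event (three rash, one hypersensitivity, one serum sickness, one asthenia).

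- Patients with Grade ≥3 rash: 0.370 × 27 ≈ 10. The proportion is 10/27 = 37.0%, exact (Clopper-Pearson) 95% CI 19.4–57.6%.
- Expected in this trial at that rate: 24 × 10/27 = 8.9 of 24 patients (24 × 0.194 = 4.7 to 24 × 0.576 = 13.8). This ignores any benefit from the antihistamine and montelukast prophylaxis in 5.1.

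**Pool in which a second episode could occur on treatment**

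Section 1.6 does not say how many of the six who discontinued were among the 10 with Grade ≥3 rash, so only bounds are available.

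- Minimum, if all six were among the 10: 10 − 6 = 4. Then 4/27 = 14.8%, exact 95% CI 4.2–33.7%, which is 24 × 4/27 = 3.6 of 24.
- Maximum, if none were: 10 − 0 = 10 of 27.

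**What cannot be computed**

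The documents give no recurrence rate and no split between Grade 3 and Grade 4. To show scale only: if an assumed 10%, 30% or 50% of the 8.9 expected patients had a second Grade ≥3 episode or a Grade 4 rash, that would be 0.9, 2.7 or 4.4 of 24. Those percentages are assumptions and are not estimates from the documents.

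**The case against.** The best defence is that the texts do different jobs. 5.4 describes how to manage a rash, and 5.2.2 sets the conditions that end cetrelimab. A hold-and-restart instruction beneath a general stopping cap is ordinary protocol structure, and the rash row never says to restart despite 5.2.2. Section 5.2.2 itself pairs a delay for Grade 3 rash with a repeat-event stop, so the stop evidently limits the delay. 5.4 also cannot be used alone, because the apalutamide dose levels it refers to appear only in 5.2.3. The explicit deferral of rash to 5.4 covers apalutamide only, which suggests that 5.2.2 still governs cetrelimab. Finally, a Grade 4 rash without any of the listed skin features may be rare, and investigators keep their general discretion to stop treatment.

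Much of this stands. Treating 5.2.2 as the cap is the more natural reading, a first Grade 3 rash raises no conflict, and the Grade 4 case may be uncommon. The 37.0% counts everyone who enters the row; it does not count those who meet the conflict.

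The argument still rests on inference. No sentence gives precedence. The rash table is the more specific text, it names cetrelimab, and its range includes Grade 4. The need to consult 5.2.3 for apalutamide dose levels does not take the reader to the cetrelimab stopping list. The recurrence case is untouched by the stops based on appearance. Discretion to stop does not make two written rules agree.

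**Conclusion.** The concern holds. Followed as written, the Grade ≥3 row of the rash table can restart cetrelimab in two situations that 5.2.2 excludes. The repeat Grade ≥3 rash is the stronger of the two, because the stops based on appearance will already catch some Grade 4 rashes.

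The number of affected patients is unknown. What can be said is that the row will be used (10 of 27 in the combination study) and that at least 4 and at most 10 of those 27 had Grade ≥3 rash without stopping for an adverse event. Carrying this over assumes that the earlier rash rate applies here, before any effect of prophylaxis.

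This is a conflict between safety instructions for the leading Grade ≥3 toxicity reported in section 1.6. It should be corrected, but it does not affect the validity of the primary analysis.

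**What to change.** Add one sentence to the Grade ≥3 row of the rash table in section 5.4:

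> Reinitiation of cetrelimab applies only to a first Grade 3 rash; at a second Grade ≥3 treatment-related rash, or any Grade 4 treatment-related rash, permanently discontinue cetrelimab (Section 5.2.2).

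Leave the 5.2.2 list and Table 5.2 as they are. If the sponsor in fact intends to allow a restart in these cases, the alternative is an explicit rash exemption in 5.2.2; either way the two sections must agree.

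The cost is one sentence in an amendment, with no added patients, visits or procedures. The drawback is that a patient who might have tolerated another restart loses cetrelimab, which 5.2.2 already requires.

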10. ECOG performance status  $\leq 1$  (Karnofsky performance status  $\geq 70\%$ , see Appendix 1)
11. Demonstrates adequate organ function as defined below:

Adequate bone marrow function:

Absolute neutrophil count	$\geq 1,500/\text{mcL}$
Platelets	$\geq 100,000/\text{mcL}$
Hemoglobin	$\geq 9.0 \text{ g/dL}$

Adequate hepatic function:

Total bilirubin	$\leq 1.5 \times$ institutional upper limit of normal, unless elevated due to Gilbert's syndrome and direct bilirubin is within normal limits
AST (SGOT)	$\leq 3 \times$ institutional upper limit of normal ( $\leq 5 \times$ ULN in presence of liver metastases)
ALT (SGPT)	$\leq 3 \times$ institutional upper limit of normal ( $\leq 5 \times$ ULN in presence of liver metastases)

Adequate renal function:

Serum creatinine	$\leq 1.5 \times$ institutional upper limit of normal
------------------	---

OR

Calculated creatinine clearance      GFR  $\geq$  30 mL/min/1.73 m^2, calculated using the CKD-EPI equation

12. Ability to understand a written informed consent document, and the willingness to sign it.
13. Patients must agree to use adequate contraception and to not donate sperm prior to the study, for the duration of study participation, and 5 months after last administration of study treatment. Adequate contraception includes (see Appendix 3 for more detail):
  - c. Patients who are sexually active should consider their female partner to be of childbearing potential if she has experienced menarche and is not postmenopausal (defined as amenorrhea  $>$  24 consecutive months) or has not undergone successful surgical sterilization.
  - d. Even participants who have undergone vasectomy should still use acceptable method of contraception.
  - e. Acceptable methods of contraception include hormonal combined (estrogen + progesterone) or progesterone only given orally, injected or implanted; IUD, IUS, tubal ligation, vasectomy and complete sexual abstinence.
14. Patients must be willing to undergo metastatic tumor biopsy during Screening if no biopsy has previously been done. If no metastatic lesion is safely accessible to tumor biopsy, this requirement will be waived. Bone or soft tissue lesion is allowed, but soft tissue will be prioritized. If a patient has archival tissue obtained within 90 days of C1D1 the requirement for fresh tumor biopsy will be waived.

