 Including complete blood cell (CBC) with differential and platelet count. All laboratory assessments have a window of +/- 3 days.

 Chemistry panel includes: sodium, potassium, chloride, bicarbonate, blood urea nitrogen (BUN)/creatinine, calcium, alkaline phosphatase (ALP), ALT/AST, total bilirubin. All laboratory assessments have a window of +/- 3 days.

 Thyroid function tests - including thyroid-stimulating hormone (TSH), with reflex free T4, total/free T3. Thyroid function tests will be performed on Day 1 of each Treatment Cycle.

 Whole Blood for peripheral immune marker assessment will be collected on C1D1 (pre-dose), C2D1 (pre-dose), C3D1 (pre-dose), and End of Treatment.

 Tumor assessment will be performed with CT Chest/Abdomen/Pelvis and whole-body bone scan during screening, C4D1 (-14d), C7D1 (-14d) and on D1 (-14d) of every 4 cycles thereafter (e.g. C11D1, C15D1). If PD by RECIST1.1/PCWG3, confirmatory scans are required ≥ 4 weeks following first scan showing progression. Lesions on chest x-ray are acceptable as measurable lesions when they are clearly defined and surrounded by aerated lung. However, CT is preferable.

 CT with contrast or MR brain is required during Screening only if history of brain metastases or clinical suspicion.

 Optional Tumor biopsy will be performed during Screening. Biopsy only required if no biopsy has previously been done. If no metastatic lesion is safely accessible to tumor biopsy, this requirement will be waived. Bone or soft tissue lesion is allowed, but soft tissue will be prioritized. If a patient has archival tissue obtained within 90 days of C1D1, and no intervening therapy between tissue acquisition and C1D1, the requirement for fresh tumor biopsy will be waived. Tumor biopsy at progression is

optional and should be the same lesion as Screening biopsy whenever feasible. Biopsy at PD also optional. Refer to Lab Manual for detail regarding tissue collection/biopsy.

 If a subject experiences a treatment-emergent rash of Grade  $\geq 2$ , consider referral to Dermatology for skin biopsy if clinically indicated per conventional (standard of care) rash management. See Section 5.4 for rash management.

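### The cetrelimab liver stopping rule for patients with a baseline Grade 2 AST/ALT elevation due to liver metastasis has a size condition that is always met, disagrees with the Grade 4 rule, and depends on a duration that no required test measures

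*Combined protocol and SAP*

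**What the plan says.** In the protocol, Section 5.2.2 lists events that require cetrelimab to be stopped permanently. Any one of them is enough, and the section closes by ruling out retreatment. Three entries matter here:

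- **Parent liver bullet.** Stop for Grade 3 or higher AST or ALT above "5xULN or total bilirubin" above 3 × ULN.
- **Liver sub-bullet.** It begins "For subjects with baseline Grade 2 elevation of AST or ALT due to liver metastasis, only Grade" and goes on to cover Grade 3 or higher values that are at least "50% of baseline for" at least "7 days will require discontinuation of study treatment".
- **Grade 4 bullet.** Stop for Grade 4 toxicity, with two exceptions: "endocrinopathies that are controlled with replacement hormones", and haematologic toxicity that clears in under 7 days. Liver enzymes are not excepted.

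Three other places fix the inputs:

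- **Section 3.3.1, item 11.** AST and ALT at entry may be up to 5 × "ULN in presence of liver metastases".
- **Table 5.2.** AST and ALT must be no higher than 5 × ULN "for patients with liver metastases" before each administration.
- **Section 6.1, footnote 3.** "Chemistry panel includes: sodium, potassium, chloride, bicarbonate, blood urea nitrogen (BUN)/creatinine, calcium, alkaline phosphatase (ALP), ALT/AST, total bilirubin", with a window of 3 days either way. The calendar and Section 6.3.2 place this panel on Cycle 1 Day 1, Cycle 1 Day 15, and Day 1 of each later 28-day cycle.

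**The concern.** The sub-bullet is meant to separate patients who must stop cetrelimab for good from those who need not, among people whose enzymes were already raised by liver disease. A rule of that kind needs a size threshold that some values fail, a duration that someone measures, and a clear rank against the other stopping rules. On its face it lacks all three. Two investigators with the same laboratory values could then reach different decisions on an irreversible step. Hepatic toxicity is a known risk: in the cetrelimab monotherapy data in Section 1.5, hepatotoxicity and ALT increase each led to discontinuation in 1 of 213 subjects. In a trial of 24 patients, even one case handled differently changes the exposure record and the count of adverse-event discontinuations.

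**Working it through.** The plan states no figure to reproduce on this point. The check is threshold arithmetic, gaps between blood draws, and a comparison of the two bullets on the same course.

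**1. Size condition.** Let b be baseline AST or ALT in multiples of ULN, and v the on-treatment value.

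- b ≤ 5 (Section 3.3.1; Table 5.2 sets the same limit before the first dose).
- v > 5 for Grade 3 or higher (parent bullet of 5.2.2).
- Threshold as written: 0.5 × b ≤ 0.5 × 5 = 2.5.
- Since v > 5 ≥ b, v/b > 1. Every Grade 3 or higher value is above 100% of baseline, so a 50% condition is always met.

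The phrase could have been meant as 50% *above* baseline, which is 1.5 × b. That line lies above the Grade 3 line only if 1.5 × b > 5, so b > 5/1.5 = 3.33. The documents give no Grade 2 range. Taking it as 3 to 5 × ULN (an assumption):

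| b (× ULN) | 50% of b | 50% above b | Does the second reading exclude any Grade 3 value? |
|---|---|---|---|
| 3.0 | 1.5 | 4.5 | No |
| 4.0 | 2.0 | 6.0 | Yes |
| 4.5 | 2.25 | 6.75 | Yes |
| 5.0 | 2.5 | 7.5 | Yes |

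Example: baseline 4.5 × ULN, ALT 6 × ULN for 10 days. The ratio is 6/4.5 = 133%. As written, this is a required permanent stop. Under the second reading 6 is below 6.75, so it is not.

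**2. Grade 4.** Take a patient in this group whose ALT reaches Grade 4 and resolves in under 7 days.

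- Grade 4 bullet: no liver exception, so a permanent stop is required.
- Liver sub-bullet: Grade 3 or higher includes Grade 4, and only rises of at least 7 days require a stop. This one does not.

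No sentence says which governs.

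**3. Duration.** With a 3-day window at each end, the gap between draws is the nominal gap ± 6 days.

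- Cycle 1, and Day 15 to Cycle 2 Day 1: 14 days, range 8 to 20.
- From Cycle 2 Day 1 onward: 28 days, range 22 to 34.

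The shortest possible gap is 8 days, so no two scheduled on-treatment draws fall within 7 days. Two consecutive Grade 3 or higher values would support a duration of at least 7 days, but late. A single Grade 3 value with recovered values on either side could reflect a rise of a few days or one of several weeks, because after Cycle 2 the neighbouring draws are nominally 28 + 28 = 56 days apart.

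**4. What the two outcomes are.** Table 5.2 bars dosing above 5 × ULN in patients with liver metastases. A patient not required to stop is therefore held until values fall, and may then resume.

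**The case against.** The best defence concerns Grade 4. The list is disjunctive, and the liver sentence is indented under the AST/ALT bullet, so it can be read as qualifying that bullet alone. The Grade 4 bullet then applies in its own right and the conflict disappears. This reading is possible, but the word only points the other way and nothing in the text settles it. The drafters wrote a short-duration exception for haematologic Grade 4 events, so they knew how to place one there. Whether its absence for liver enzymes was deliberate cannot be told.

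It can also be said that a visit calendar need not list event-driven tests, that investigators may repeat abnormal results, and that enzymes must be rechecked before re-dosing. This stands in part. The permission to repeat is discretionary and sits in the screening paragraph of Section 6. Section 7.3.5 follows adverse events to resolution but gives no laboratory interval. A pre-dose check shows recovery, not how long the rise lasted.

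Some stronger readings are tempting but not supported:

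- *The schedule makes the 7-day condition impossible to assess.* Two consecutive scheduled values or a discretionary repeat could show it. What is missing is a required repeat.
- *Patients could go on receiving drug with high enzymes.* Table 5.2 prevents that.
- *The defect affects all patients with liver metastases.* The sentence covers only those with a baseline Grade 2 elevation due to liver metastasis.
- *Different sites would diverge.* Appendix 2 is headed as single site; the issue is between investigators or occasions.
- *PFS would be biased through censoring.* Section 5.2 lets the other drug continue, and Section 8.3.3 does not say that stopping cetrelimab alone triggers censoring.

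**Conclusion.** The concern holds in a limited form: the sub-bullet does not work as written. The size condition filters nothing, the rule for a short Grade 4 rise is contradictory on its face, and the duration condition is not tied to any required test.

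The first result rests on the protocol's own pairing of Grade 3 with more than 5 × ULN and on its 5 × ULN cap. It does not depend on the assumed Grade 2 range, which is used only to illustrate the alternative reading. The documents do not reproduce the CTCAE cut-offs, and none were relied on.

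Few patients are likely to be affected. Grade 3 or higher AST and ALT increases occurred in 3.3% and 2.8% of the 213 monotherapy subjects. Applied to 24 patients, that is 24 × 0.033 = 0.8 and 24 × 0.028 = 0.7. These are rates for all monotherapy subjects, not for the subgroup or the combination, and the documents give no subgroup figure. The reason to correct the text is that the decision is permanent and the wording gives two answers, not that many cases are expected.

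**What to change.** The sponsor and medical monitor should reconcile five places: the liver sub-bullet in 5.2.2, its parent bullet, the Grade 4 bullet, Table 5.2, and the chemistry schedule in Sections 6.1 and 6.3.2. The revised text should make three things clear:

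1. What the 50% is measured against, worded so that the condition is not empty.
2. Which single rule governs a Grade 4 AST or ALT elevation in this group.
3. How the duration condition corresponds to tests that the protocol requires.

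Which clinical rule is right is for them to decide; this review takes no position. The cost is protocol wording only, or at most an occasional repeat chemistry in the few patients concerned. Sample size and the analysis plan do not change.
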